The Vineland-3 measures 5 domains of adaptive functioning: communication, daily living skills, socialization, motor skills, and maladaptive behaviors. The Vineland-3 is published by the WPS Publishing company and is subject to copyright laws, therefore, it cannot be uploaded.	[contact]	07/30/2023 19:35:41
The ASQ:SE-2 evaluates seven areas of social-emotional functioning in children ages 1 - 72 months: self-regulation, compliance, social-communication, adaptive functioning, autonomy, affect, and interaction with people. The ASQ: SE-2 is published by the Brooks Publishing company and is subject to copyright laws, therefore, it cannot be uploaded.	[contact]	07/30/2023 19:35:41
The Ages and Stages Questionnaire, 3rd edition, used for children ages 1 - 66 months and assesses gross motor, fine motor, communication, problem-solving, and personal-social development. The ASQ-3 is published by the Brooks Publishing company and is subject to copyright laws, therefore, it cannot be uploaded.	[contact]	07/30/2023 19:35:41
The Strengths and Difficulties Questionnaire (SDQ) is a brief behavioral screening questionnaire about 3-16 year-olds. It exists in several versions for differing ages to meet the needs of researchers, clinicians and educationalists. The initial Strengths and Difficulties Questionnaire(SDQ) will be used on participants ages 3 - 17 years to assess psychological attributes in the following categories: emotional symptoms, conduct problems, hyperactivity/inattention, peer relationship problems, and prosocial behaviors. The Strengths and Difficulties Questionnaire published by Youth in Mind and is subject to copyright laws, therefore, it cannot be uploaded.	[contact]	07/30/2023 19:35:41
The O'HAIRE canine behavior ethogram will be used to assess human-animal interaction. The manual is too large to upload and is available upon request.	[contact]	07/30/2023 19:35:41
The Autism Diagnostic Observation Schedule-Second Edition (ADOS-2) is a standardized assessment tool that helps providers diagnose autism spectrum disorders (ASD) in children and adults. The ADOS involves a semi-structured play or interview session determined by the age and communication level of the individual. The ADOS provides standardized activities and questions that give the examiner opportunities to observe behaviors that are directly relevant to the diagnosis of ASD. The ADOS-2 incorporates the use of planned social activities designed for different developmental levels and	[contact]	07/30/2023 19:35:41

Protocol Number: 2307483365
Investigator: [name]

Expiration Date:
Last Approval Date: 10/11/2024

Protocol Notes

Comment	By	Time
chronological ages that provide situations in which social interactions, communication and particular types of behaviors are likely to appear. The examiner chooses from five different modules depending on age (12 months through adulthood), language and developmental level. The assessment usually takes 40 - 60 minutes to complete. The examiner scores the ADOS-2 based on observations noted during the session on several aspects of social behavior. The score on the ADOS-2 indicates whether or not the individual's presentation is consistent with a diagnosis of an ASD. The ADOS-2 is published by the WPS Publishing company and is subject to copyright laws, therefore, it cannot be uploaded.		
The Childhood Autism Rating Scale-Second Edition (CARS2) is a 15-item rating scale used to identify children with autism and distinguishing them from those with developmental disabilities. It is empirically validated and provides concise, objective, and quantifiable ratings based on direct behavioral observation. It was normed on a sample of 1,034 individuals with autism spectrum disorders. This second edition of CARS expands the test's clinical value, making it more responsive to individuals on the "high functioning" end of autism spectrum disorders. The clinician rates the individual on each item, using a 4-point rating scale. Ratings are based on frequency of the behavior in question, its intensity, peculiarity, and duration. The CAR2 is published by the WPS Publishing company and is subject to copyright laws, therefore, it cannot be uploaded.	[contact]	07/30/2023 19:35:41

Actions

Description	Comments	Action Date
Expedited Approval	Renewal-001: Approved	10/11/2024
Expedited Approval	Renewal-001:	10/11/2024
Assigned to Agenda	Renewal-001:	10/11/2024
Submitted to IRB	Renewal-001: Submitted to IRB	09/21/2024
Renewal Created	Renewal-001: Created	09/21/2024
Renewal Reminder Generated	Renewal Reminder Letter #2	08/20/2024
Renewal Reminder Generated	Renewal Reminder Letter #1	07/05/2024
Expedited Approval	Amendment-001: Approved	04/26/2024
Expedited Approval	Amendment-001:	04/26/2024

Protocol Number: 2307483365
Investigator: [name]

Expiration Date:
Last Approval Date: 10/11/2024

Actions

Description	Comments	Action Date
Assigned to Agenda	Amendment-001:	04/26/2024
Submitted to IRB	Amendment-001: Submitted to IRB	04/14/2024
Amendment Created	Amendment-001: Created	04/14/2024
Expedited Approval		09/19/2023
Assigned to Agenda		09/19/2023
Administrative Correction	Changing consent document format to PDF for approval watermark.	09/19/2023
Submitted to IRB	Submitted to IRB	09/05/2023
Specific Minor Revisions Required		09/05/2023
Delete Review	Online reviewer [name] has been deleted. Deletion reason - Reviewer has not responded in a reasonable length of time; review is being reassigned to another board member.	08/25/2023
Submitted to IRB	Submitted to IRB	07/30/2023
Protocol Created	Protocol created	07/29/2023

Review Comments

Protocol Number: 2307483365 **Sequence Number:** 3
Principal Investigator: [name]
Title: Human animal interaction between children with ASD and a live canine or plush toy dog
Committee Id: 200 **Committee Name:** IRB Expedited Review
Schedule Id: 45832 **Schedule Date:** 11/16/2024

Review Comments:

Positive and Negative Affect Schedule (PANAS-SF)

Indicate the extent you have felt this way over the past week.		Very slightly or not at all	A little	Moderately	Quite a bit	Extremely
PANAS 1	Interested	 1	 2	 3	 4	 5
PANAS 2	Distressed	 1	 2	 3	 4	 5
PANAS 3	Excited	 1	 2	 3	 4	 5
PANAS 4	Upset	 1	 2	 3	 4	 5
PANAS 5	Strong	 1	 2	 3	 4	 5
PANAS 6	Guilty	 1	 2	 3	 4	 5
PANAS 7	Scared	 1	 2	 3	 4	 5
PANAS 8	Hostile	 1	 2	 3	 4	 5
PANAS 9	Enthusiastic	 1	 2	 3	 4	 5
PANAS 10	Proud	 1	 2	 3	 4	 5
PANAS 11	Irritable	 1	 2	 3	 4	 5
PANAS 12	Alert	 1	 2	 3	 4	 5
PANAS 13	Ashamed	 1	 2	 3	 4	 5
PANAS 14	Inspired	 1	 2	 3	 4	 5
PANAS 15	Nervous	 1	 2	 3	 4	 5
PANAS 16	Determined	 1	 2	 3	 4	 5
PANAS 17	Attentive	 1	 2	 3	 4	 5
PANAS 18	Jittery	 1	 2	 3	 4	 5
PANAS 19	Active	 1	 2	 3	 4	 5
PANAS 20	Afraid	 1	 2	 3	 4	 5

Scoring:

Positive Affect Score: Add the scores on items 1, 3, 5, 9, 10, 12, 14, 16, 17, and 19. Scores can range from 10 – 50, with higher scores representing higher levels of positive affect.
Mean Scores: 33.3 (SD \pm 7.2)

Negative Affect Score: Add the scores on items 2, 4, 6, 7, 8, 11, 13, 15, 18, and 20. Scores can range from 10 – 50, with lower scores representing lower levels of negative affect.
Mean Score: 17.4 (SD \pm 6.2)

Your scores on the PANAS: Positive: _____ Negative: _____

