Participants were divided into two groups: one with a therapy canine and one with a plush toy dog. Therapy sessions lasted 30 to 45 minutes, depending on the age and ability of the participant. All participants, no matter their group, received the same therapeutic strategies, such as sensory integration therapy and seated activity with the therapist, who is a certified pediatric nurse practitioner. Sessions with the therapy canine started with five to 10 minutes of free play with the canine, followed by sensory integration therapy based on the child's identified sensory profile. Participants then entered the clinic room for 20 to 30 minutes of a seated activity in which the therapist who taught coping and socialization strategies to participants and caregivers. Sessions concluded with five minutes of play with the canine. Play activities include fetch, soccer, hide and seek, and puzzles. The canine was trained to lay under the table in the clinic room while the therapist was working with the participants. He would provide grounding, light pressure, and deep pressure therapy if the participant became anxious during the sessions. The seated work was recorded using two cameras to ensure visibility of the interactions between the participant and therapist, canine, and caregiver; participant vocalizations and verbalizations; and participant facial expressions. We used two human-animal ethograms to code behavior during sessions and two behavioral assessments to note behavior occurring after sessions. All sessions occurred in the clinic located on the university's campus. Demographic data including participant age, gender, race, ethnicity, referral source, prior medical diagnoses, age of ASD diagnosis, medications, and prior allied health, school, or psychological evaluations. The canine was certified as a therapy dog and service dog certified in 10 ASD service dog tasks at the time of the study. The canine was present during sessions to interact with children and assist them to practice and develop skills to address identified deficits in social-emotional and adaptive functioning, prosocial behavior, and emotional regulation. AAT sessions were recorded to code interactions at a later time.

Objectives

This study will address the following research questions:

1. How do children with autism ages 2 to 18 years interact with a live canine during AAT sessions?
2. How do children with autism ages 2 to 18 years interact with a toy plush dog during AAT sessions?

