3. Is there a difference in HAI in the live canine group and the toy plush dog group?
4. Is there a difference in prosocial behavior observed during AAT sessions between the live canine group and the toy plush dog group?
5. Is there a difference in behavior after AAT sessions between the live canine group and the toy plush dog group?

Design and Statistical Analysis Plan

We used two human-animal ethograms to investigate human-animal interaction and bonding occurring during AAT sessions. Prosocial behavior and emotional regulation demonstrated by participants outside of AAT sessions were assessed by two self-report questionnaires completed by caregivers. SPSS and Microsoft Excel were used to calculate the analysis. Descriptive statistics were utilized to compare prosocial behavior and emotional regulation occurring apart from AAT sessions between the two groups. Poisson analysis was conducted to examine human-animal bonding and human behavior occurring during AAT sessions. Independent *t*-tests were used to analyze the differences in human-animal interaction between the two groups. The homogeneity of the variance (HOV) assumption between two groups was checked using Levene's test for equality of variances in SPSS program before conducting the *t*-tests analysis. Results of *t*-tests with adjusted degrees of freedom value were reported if the HOV was violated. The null hypothesis was set to reflect no significant difference in HAI between groups for the independent *t*-tests; therefore, a significant difference in the human-animal interaction and human behaviors regarding the inclusion or exclusion of the canine could be confirmed if the *t*-test results reject the null hypothesis. Cohen's *d* was used to report the effect sizes of the independent *t*-tests; values up to 0.20 were interpreted as small, 0.50 as medium, and 0.80 as large effect sizes. Analysis of variance was used to assess differences between the two groups in prosocial behavior and emotional regulation occurring apart from AAT sessions.

Methods

Demographic data; past, family, and social histories; and prior therapy evaluations were collected during the initial consultation for enrollment into the ASD program. Additionally, pet ownership in the family home was included in the analysis.

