Lastly, the Positive and Negative Affect Schedule (PANAS) was administered weekly to measure therapeutic effects occurring in everyday life outside of the AAT session. The PANAS is a 20-item questionnaire utilizing a 5-point Likert scale to assess positive and negative affect occurring the week prior to administration. Each domain has 10 items with scores ranging from 10 to 50, with lower scores reflecting lower levels of positive or negative affect and higher scores signifying higher positive or negative affect. Total scores on each scale are obtained by adding the scores for each item. Analysis of the PANAS demonstrates very good internal consistency reliability, with alphas ranging from 0.86 to 0.90 for Positive affect and from 0.84 to 0.87 for Negative affect.

Protocol Number: 2307483365
Investigator: [name]

Expiration Date: 10/10/2025
Last Approval Date: 10/11/2024

University of Arkansas System

Document Overview

Description: Human animal interaction between children and a live canine or toy plush dog
Explanation:
Organization Doc Num:

Protocol Summary

Protocol Number: 2307483365
Sequence Number: 3
Status: Active - Open to Enrollment
Expiration Date: 10/10/2025
Last Approval Date: 10/11/2024
Investigator: [name]

Protocol Details

Type: Expedited
Summary/Keywords:
Application Date: 09/21/2024
Reference ID1:
Reference ID2:
FDA Application No:
Title: Human animal interaction between children with ASD and a live canine or plush toy dog

Areas of Research

Code	Description
000001	All Research Areas

Organizations

Type	Organization	Address
Performing Organization	University of Arkansas	University of Arkansas [name] USA

Funding Source

Type	Number/Code	Source	Title
Internally Funded/ Unfunded Research	unfunded	N/A	

Protocol Number: 2307483365
Investigator: [name]

Expiration Date: 10/10/2025
Last Approval Date: 10/11/2024

Subjects

Subject	Count
Children	150

Investigators

Person Name: [name] **Role:** Principal Investigator
Units: CC012723 UAF | NURS | Department of Nursing **Affiliation:** Supervisor
Office [contact] **Mobile:**
Email: [contact]

Study Personnel

Person Name	Role	Affiliation	Email
[name]	Study Personnel	Non-Faculty	[contact]
[name]	Study Personnel	Student Investigator	[contact]
[name]	Study Personnel	Student Investigator	[contact]

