
- **How long are the procedures likely to take? Include duration and frequency.**

The A4A weekly therapy sessions will last about 30 to 60 minutes, with opportunities for participants to interact with the canine or toy plush dog intermittently throughout the session, depending on the therapy activity.

- **How will information be given to people to get their informed consent to participate in this research? Answers should include specific methods (e.g., verbal consent, information handout, online consent form, full consent form requiring signature documentation.) **Please note that consent materials -- from a script for verbal consent to full consent forms that require participant signature -- must be uploaded in the Notes and Attachments section.**

[name] will contact parents/guardians of potential participants to explain the AAT program and gage their interest. If interested, parents will come to the A4A clinic on the first floor of ECHP to meet the canine and sign the informed consent form. Verbal assent will be obtained from pediatric patients who are cognitively able to give it.

- **Does data collection rely on a scheduled event, such as a convention or specific date?**

No

- **How will your data be collected? Include all that apply: online, on paper/in person, audio and/or video recordings. **Please note that all data collection materials will need to be uploaded in the Notes and Attachments section. This includes: surveys, questionnaires, interview questions or anything that is given to or asked of a participant.**

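### The PANAS and SDQ recall windows include the weekly AAT sessions, so neither outcome can be described as affect or behavior apart from sessions

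*Combined protocol and SAP*

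**What the plan says.** The Methods section says that the PANAS "was administered weekly to measure therapeutic effects occurring in everyday life outside of the AAT session". The Design and Statistical Analysis Plan says that prosocial behavior and emotional regulation "outside of AAT sessions were assessed by two self-report questionnaires completed by caregivers", and it uses analysis of variance to assess "differences between the two groups in prosocial behavior and emotional regulation occurring apart from AAT sessions".

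The instruments ask something broader. The PANAS-SF form attached to the IRB application carries one instruction on timing: "Indicate the extent you have felt this way over the past week". The Methods section agrees that the PANAS is used to "assess positive and negative affect occurring the week prior to administration". It gives the SDQ a window of the preceding four weeks, with follow-up forms every four weeks.

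On the sessions themselves, the IRB application states: "The A4A weekly therapy sessions will last about 30 to 60 minutes". The study description gives a somewhat shorter length: "Therapy sessions lasted 30 to 45 minutes, depending on the age and ability of the participant". It also says that the therapist "taught coping and socialization strategies to participants and caregivers" during the seated part.

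No section asks the respondent to disregard the session, fixes when a form is completed relative to it, or separates the two in the analysis.

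**The concern.** Of the five research questions, only question 5 concerns behavior after sessions. Questions 3 and 4 already cover what happens within them. If the question 5 outcomes also take in session time, a child who enjoys the session more with a live dog, and is unchanged at home, can score differently on the PANAS or SDQ. The report would then present the same in-session response a second time as an effect in everyday life.

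Both groups have sessions in the window, so bias in the comparison requires in-session affect to differ between groups. That is the difference questions 3 and 4 set out to find, so it cannot be assumed absent. Several PANAS items (Excited, Enthusiastic, Active) describe states that play with a dog could plausibly raise.

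**Working it through.** The plan gives no power, alpha or bias figure on this point, so there is nothing of its own to reproduce.

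**Inputs from the documents**
- PANAS window: 7 days (form and Methods). SDQ window: four weeks (Methods).
- Sessions: weekly, 30 to 60 minutes (IRB application).
- PANAS score range: 10 to 50 per domain, a span of 40 points (Methods).
- Positive affect SD: 7.2 (scoring note on the form).
- Planned number of children: 150 (IRB application).

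**Assumptions**
- 75 per group, which is half of 150 (no split is stated); 40 and 20 per group are shown as alternatives.
- 12 waking hours a day.
- A two-sided 5% test on one comparison of group means, with no true difference outside sessions.

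**1. Does the window contain a session?** With a session every 7 days, a 7-day look-back contains 7/7 = 1 session, whichever day the form is completed. The SDQ window contains about 28/7 = 4. The exceptions are a form completed before the first session or after a missed one.

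**2. Low end: ratings weighted strictly by time.**
- Minutes in a week: 7 × 24 × 60 = 10,080. Waking minutes: 7 × 12 × 60 = 5,040.
- Session share of the whole week: 30/10,080 = 0.30% to 60/10,080 = 0.60%.
- Session share of waking time: 30/5,040 = 0.60% to 60/5,040 = 1.19%.
- Largest possible shift, with the session at one end of the scale and the rest of the week at the other: 40 × 60/5,040 = 0.48 points.
- In SD units: 0.48/7.2 = 0.07.
- Noncentrality at 75 per group: (0.476/7.2) × √(75/2) = 0.40. The two-sided noncentral-t probability of significance is 6.9%, against 5% nominal.

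**3. Higher range: recall not weighted by time.** Suppose that recall of the session raises one, two or three positive items by one category each, in one group only. The standardized difference is the shift divided by 7.2. The last three columns give the probability of a significant result.

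| Shift (points) | Shift in SD | 75 per group | 40 per group | 20 per group |
|---|---|---|---|---|
| 1 | 1/7.2 = 0.14 | 14% | 9% | 7% |
| 2 | 2/7.2 = 0.28 | 39% | 23% | 14% |
| 3 | 3/7.2 = 0.42 | 72% | 45% | 25% |

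The smaller group sizes matter because the IRB application's list of instruments gives the PANAS for ages 9 to 14, while the study covers ages 2 to 18. If that range was applied, fewer children have PANAS data.

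No matching calculation is made for the SDQ, because the documents give no SD for it. Step 1 applies to it all the same.

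**The case against.** The strongest reply is that the bias may be negligible. A session takes up about 1% or less of the week, both groups have one, and both receive the same therapeutic strategies. On a time-weighted reading the excess over the nominal 5% is about two percentage points. The shifts of 1 to 3 points are chosen, not estimated, and the SD is the form's printed value, whose fit to this sample is not shown. All of this stands, and it is why no single figure should be taken as the size of the bias.

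A reader might go further and infer that in-session affect is being counted as carry-over, because caregivers watch the play with the dog and remember it vividly. The documents do not support that. They place caregivers in the seated activity, when the dog was trained to lie under the table, and do not say that caregivers attend the free play. The form also addresses the respondent in the second person, which leaves some doubt about who answers, although the analysis plan says caregivers do. What is established is that in-session affect is eligible to be counted, not that it is counted or how heavily.

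It can also be said that an added instruction comes too late, since the study description dates the study from June 2022 to August 2024, and that asking people to discount one session is untested. The first part holds for forms already collected, although the IRB record still shows the study open to enrollment. Neither part bears on the description of the results, which can be corrected without new data.

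**Conclusion.** The mismatch between the stated outcome and the two instruments holds, and no text in the documents resolves it. The PANAS and SDQ measure affect and behavior over one week and four weeks with sessions included. A group difference on either cannot by itself be attributed to life outside sessions.

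The size of any resulting bias is unknown. For positive affect it runs from at most 0.07 SD under strict time weighting (12 waking hours a day assumed) to 0.42 SD if session recall adds 3 points in one group only. At an assumed 75 per group the corresponding probabilities of a false significant result run from about 7% to 72%, and they are lower with fewer children. The upper figure is the consequence of an assumed shift, not a finding about this trial. The correction is worth making whatever the size, because the present description claims something that the forms did not ask.

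**What to change.** For data already collected, describe the PANAS result as affect over the past week including the session, and the SDQ result as behavior over the past four weeks including sessions. Remove from the question 5 conclusion, and from the Methods and analysis-plan descriptions of these outcomes, the wording that places them outside or apart from AAT sessions. This needs no new data and no new analysis. Its cost is a narrower conclusion: question 5 can no longer be answered as pure carry-over.

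For any future forms, add one line above the items of both questionnaires, identical in both groups, for example: Please do not count time spent in the therapy session, with the dog or the toy. The cost is one line and a small departure from the printed instruction. Whether respondents can fully set the session aside is not shown, so the report should say that they were asked to, not that session time was removed.
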